5.4.2.4 Treatment response as assessed by change in PSA

Baseline PSA is the most recent PSA measurement prior to salvage therapy for subjects who had salvage treatment and the most recent PSA measurement prior to the ^{18}F -fluciclovine PET/CT for non-salvage subjects. Treatment response, which is based on the percentage change in PSA from baseline to the last value reported, is defined as:

- $\geq 30\%$ decrease in PSA will be considered to be a response to treatment
- $<25\%$ increase or $<30\%$ decrease will be classified as stable disease
- $\geq 25\%$ increase in PSA will be classified as disease progression

The number, percentage and exact 95% CI of subjects having a treatment response, stable disease and disease progression, as assessed by change in PSA, will be presented overall and separately for subjects in the EAS who had salvage treatment, for subjects who had non-salvage treatment, for those with a change in management plan and for subjects with no change in management plan, by treatment and by disease location (Local disease/Extra-prostatic disease) following the ^{18}F -fluciclovine PET/CT scan.

In addition, the percentage change in PSA from baseline to the last value reported will be summarised overall and by subjects who had a change in management plan versus those who did not have a change in management plan following the ^{18}F -

fluciclovine PET/CT scan. The percentage change in PSA from baseline to the last value reported will also be summarised for subjects who had disease in the prostate only and for subjects who have extra-prostatic disease and by treatment.

Finally, a waterfall plot of the maximum percentage reduction in PSA during the 4-8 month window will be presented on the y-axis and each subject will be represented by a bar on the x-axis. The bars will be ordered in descending order of the magnitude of the percentage change in PSA value.

Treatment response and the factors used to assess the response will be listed in full.

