9.2 Clinical Assessments

Data from the following assessments and procedures should be documented in the Subject's medical records and recorded in the eCRF

1. Concomitant Medications

All concomitant medication and concurrent therapies will be documented at Screening and at all Visits and at End of Follow up. Dose, route, unit frequency of administration, and indication for administration and dates of medication will be captured.

2. Demographics

Demographic information will include age, gender, race and ethnicity.

3. Medical History

Include history of prostate cancer and prostate cancer treatments, and other clinically significant diagnoses. Prostate cancer history should include the date of initial diagnosis, initial tumor stage and Gleason score, dates of definitive therapy and adjuvant treatment (if given), and date of diagnosis of biochemical recurrence.

4. Imaging Studies

Imaging data will include all imaging results (including relevant bone scans, CT etc) from 60 days before screening so the final follow-up and all prostate cancer imaging results available from the Subject's file

5. Vital Signs

Blood pressure and pulse rate will be performed after resting for 5 minutes.

6. 12 lead Electrocardiogram (EKG)

EKG will be recorded as indicated in Section 10. Original EKGs are to be anonymized and forwarded to Clinical Research, Blue Earth Diagnostics, [name] and copies maintained in the Subject's medical record.

7. PSA Levels

PSA levels will be recorded from the Subjects medical records

8. Management Plan

The Intended Management Plan. The treating physician will complete the Management Plan Questionnaire to document his/her intended treatment including planned radiation fields, intended resection limits of surgery, use of brachytherapy, cryotherapy or HiFU, intended use of adjuvant therapy.

The Revised Management Plan. Where an additional diagnostic procedure (e.g., imaging or biopsy) is performed in light of the PET/CT findings, the results of these should be considered prior to recording the revised management plan. Any such diagnostic procedures do not qualify as a "change" to clinical management. The treating physician will complete the Management Plan Questionnaire to document changes to the Pre-scan Management Plan. Changes include such responses as change to radiation or surgical fields. The patient may enter another clinical trial as part of the Revised Management Plan.

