10.6 End of Study (26+/-4 weeks post scan)

The treating physician will complete the Management Plan Questionnaire to document the actual treatment given, including any changes to radiation, surgery, or medications given.

The following data from Visit 2 through to 6 months after the ¹⁸F-fluciclovine PET/CT will be abstracted from the Subject's medical record:

1. All PSA results.
2. All biopsy results and reports.
3. Restaging procedure results (e.g. bone scan or CT/MRI scans).
4. Current prostate cancer status and date of recurrence if applicable.
5. Adverse events reported by the patient
6. Date and cause of death if applicable.

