Appendix 1: Schedule of Events

	Visit 1 - Screen up to 30 days before Visit 2	Document Initial Management Plan	Visit 2 - Day of ¹⁸ F-fluciclovine PET/CT				Visit 3	Document Post 18F-Fluciclovine PET/CT Management Plan	End of Study
			Pre-dose/pre-scan	Immed. post scan	60 min post dose	120 min post dose			
Study Day	-30 to Visit 2	Prior to Visit 2	1				2	2-22	180 ± 28 days
Visit Location/Type	Treating Physician Office	NA	PET/CT Imaging Center				Phone Call	NA	NA
Assessments/Procedures									
Informed consent	X								
Inclusion/ exclusion criteria	X		X						
Medical history	X		X						
PCa history, including treatment	X								
Record PSA levels ¹	X								X
Record imaging studies ²	X								X
Vital signs (heart rate and blood pressure)	X		X	X	X	X			
Height, weight			X						
Serum chemistry and hematology	X			X ³					
Serum PSA	X								
Urinalysis, dipstick	X ⁴								
EKG			X	X ³					
Record biopsy results, if applicable									X
Injection site assessment			X	X	X	X	X		
AE assessment				X	X	X	X		X
Concomitant medication assessment	X		X						X
Document management/plan		Plan						Revised	Actual
Treatment response assessment									X

1 - Record all available PSA levels obtained prior to Visit 1 through End of Study; for non-prostatectomy subjects, the PSA nadir and 2 times over nadir result must be documented in the record.

2 - Record all available imaging studies performed prior to Visit 1 through End of Study; negative or equivocal imaging within 60 days of Visit 1.

3 - Post-dose blood tests and EKG may be performed at the Imaging Center or within 7 days of the scan at another laboratory/site. *May be collected and tested at any time between screening and scan date

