3.2 Study Design

This is a phase IIIb open-labelled, multi-centred study to assess the impact on subject management of ^{18}F -fluciclovine PET/CT in subjects with rising prostate specific antigen (PSA) after initial cancer treatment.

The prospective study will enrol up to 330 men with PSA-recurrent prostate cancer after curative-intent primary therapy and negative or equivocal findings on standard-of-care imaging. Consenting participants will be imaged with ^{18}F -fluciclovine PET/CT. Site clinicians will manage study subjects per standard practices and will document any change in treatment based on review of the ^{18}F -fluciclovine PET/CT findings. Additionally, as clinically indicated, optional biopsy will be performed. All participants will be followed for up to 6 months, with clinical data collected for this study: PSA measurement from scan for 6 months. Treatment response will be assessed 6 months post scan.

The summary flowchart of the study design is as follows:

STUDY SCHEMA

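### PSA response is classified from the last recorded value with no earliest date, although the plan elsewhere places response assessment at about 6 months

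*SAP*

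**What the plan says.** The plan gives PSA response more than one time base.

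- **Response category (SAP 5.4.2.4).** "Treatment response, which is based on the percentage change in PSA from baseline to the last value reported". A fall of at least 30% is a response, a rise of at least 25% is progression, and anything between is stable disease. No earliest date is given.
- **Baseline (same section).** "Baseline PSA is the most recent PSA measurement prior to salvage therapy for subjects who had salvage treatment". For the others it is the latest value before the scan.
- **Waterfall plot (same section).** It shows the "maximum percentage reduction in PSA during the 4-8 month window". The text does not say whether the months run from the scan or from treatment start.
- **Study design (SAP 3.2).** "Treatment response will be assessed 6 months post scan".
- **Schedule of Events (protocol Appendix 1).** The row "Treatment response assessment" is marked only under End of Study, at 180 ± 28 days. Protocol 10.6 gives that visit as 26 ± 4 weeks.
- **Source of the values (protocol 9.2, item 7).** "PSA levels will be recorded from the Subjects medical records". The schedule has one serum PSA draw, at screening.
- **Missing data (SAP 2 and 5.4.3).** Nothing is imputed.

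**The concern.** A PSA category means little without the time at which it was reached. Under 5.4.2.4 as worded, one subject may be classified on a value a few weeks after the scan and another on a value at 6 months, and both enter the same row of the same table. The plan would not show this, because no table of PSA timing is specified.

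The category is presented with exact confidence intervals for subjects with and without a change in management plan, for salvage and non-salvage treatment, and by disease location. Percentage change in PSA is also summarised for changed against unchanged plans. If the timing of the last PSA differs between such groups, part of any difference in response reflects when blood was taken. The table and the waterfall plot can also disagree for the same subject, since one uses the last value and the other the largest reduction inside a window.

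**Working it through.** The documents give no figure that depends on this rule, so there is nothing to reproduce. The check sets the time bases side by side and then illustrates the effect.

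**1. Time bases, in days after the scan** (30.4375 days per month)

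| Source | Stated | Days |
|---|---|---|
| Protocol 10.6, End of Study | 26 ± 4 weeks | 22 × 7 = 154 to 30 × 7 = 210 |
| Schedule of Events, End of Study | 180 ± 28 days | 152 to 208 |
| SAP 5.4.2.4, waterfall plot | 4-8 months, origin not stated | 122 to 244 if counted from the scan |
| SAP 5.4.2.4, response category | last value reported | no lower limit |

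The category does have an upper limit. Protocol 10.6 abstracts PSA up to 6 months after the scan (6 × 30.4375 = 183 days), and footnote 1 of the schedule extends this to End of Study. What is missing is the lower limit.

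**2. Can an early last value occur?** Yes. The Evaluable Analysis Set, on which the category is reported, requires a scan, an intended plan and a revised plan (SAP 4.1). The revised plan is due on days 2-22. No later PSA is needed to enter the set, and protocol 10.8 keeps data from withdrawn subjects whose baseline measures are complete.

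**3. No PSA after treatment start.** For a salvage subject, let *x* be the latest PSA before therapy, which is the baseline. If no later PSA is on record, the last value is also *x*, and the change is (x − x)/x = 0%. That falls in the stable-disease band. Nothing in 5.4.2.4 makes the subject not evaluable.

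**4. Illustration of an early value.** Assume PSA falls exponentially from treatment start with half-life *h* months, so that change = 0.5^(t/h) − 1. The documents give no PSA kinetics; *h* is an assumption. Time on treatment to reach a 30% fall is h × ln(1/0.7)/ln 2 = 0.515h.

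| Assumed h (months) | Months to a 30% fall | Change at 1 month on treatment | Change at 5.5 months on treatment |
|---|---|---|---|
| 1 | 0.5 | −50% | −98% |
| 2 | 1.0 | −29% | −85% |
| 3 | 1.5 | −21% | −72% |
| 4 | 2.1 | −16% | −61% |
| 6 | 3.1 | −11% | −47% |

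Take a subject who starts treatment 0.5 months after the scan. A last PSA at month 1.5 gives stable disease for every *h* from 2 to 6. A PSA at month 6 gives response for all of them. At h = 1 both values give response.

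**5. What a 6-month rule does not cure.** Let treatment start at week 6 or week 16 (assumed) with a PSA at week 26. Time on treatment is 26 − 6 = 20 or 26 − 16 = 10 weeks. If that PSA is the last one, both rules select it and the result is the same. With a start at month 4, a PSA at month 6 shows −50% (h = 2) and −37% (h = 3), but still only −29% (h = 4) and −21% (h = 6).

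**The case against.** The strongest reply is that the passages can be read together: response is assessed at the 6-month review from the latest PSA then on file. With collection closing at about 6 months, the last value is the closest available to that date for anyone whose PSA was measured regularly. The rule also keeps everyone with a PSA in the table, whereas a window drops subjects, perhaps selectively. The pre-therapy baseline is sensible, since it stops an untreated rise from counting against response. The factors used to assess response will be listed. PSA response is not among the objectives or the secondary variables in SAP 5.2, and no between-group test is planned.

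Most of this stands and limits the importance of the point. It does not supply the missing lower limit or deal with the zero-change case, and a listing is not a timing summary.

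A reader might infer more than the documents support:

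- **That the last-value rule is what penalises late starters.** It is not. Both rules run from the scan, and step 5 gives the same time on treatment under each.
- **That a changed plan delays treatment and so looks less effective.** The documents give no treatment start times and do not say this. Neither the presence nor the direction of a bias is shown.
- **That the category feeds the standard of truth.** Protocol 14.2 includes clinical response to treatment in what the Adjudication Panel compares, but nothing says that the panel uses this PSA category.

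**Conclusion.** The point holds as an inconsistency within the plan plus a missing lower time limit. Response is said to be assessed at 6 months or End of Study but is classified from a value that may be much earlier, and the same section uses a different window and a different summary for the plot. Subjects with an early last PSA, including prompt starters, can be called stable too soon, and a salvage subject without a PSA after treatment start can be called stable on no evidence.

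The number affected is unknown, because the documents give neither PSA dates nor treatment start times. The illustration rests on an assumed exponential fall and an assumed half-life; at 1 month's half-life a value one month after treatment start already counts as response. The analysis is descriptive, and the primary endpoint and the sample size are untouched. This is a worthwhile low-cost improvement, not a threat to the trial's main conclusion.

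**What to change.** Reconcile SAP 3.2, SAP 5.4.2.4 and the Schedule of Events, and settle the following in the SAP before database lock:

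1. Classify response from the PSA closest to 6 months post scan within one stated window. The section's own 4-8 months would serve, with the scan named as its origin. Counted that way it runs to day 244, while collection ends by day 210 at the latest, so its upper end would be empty.
2. Require that value to post-date the baseline value and, for treated subjects, the start of treatment.
3. Report subjects without such a value as not assessable, and state whether they stay in the denominator, since SAP 2 defaults to the whole analysis set.
4. Tabulate time from baseline, and from treatment start, to the PSA used, by change and no-change group.
5. Keep the last-value version as a sensitivity table.

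The cost is SAP wording and programming, with no new data collection. The downside is that some subjects become not assessable. The change does not equalise time on treatment for late starters; the timing table only makes the difference visible.

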5.4.3 Handling of Dropouts or Missing Data

Subjects who withdrew from the study prior to completion will be summarised. Withdrawn subjects will not be directly replaced and no imputation of missing data will be conducted

5.4.4 Interim Analyses and Data Monitoring

No interim analysis is planned for this study.

5.4.5 Examination of Subgroups

No subgroup analyses will be conducted during the study.

6 SAFETY EVALUATION

All safety evaluations will be performed on the safety analysis set (SAF) unless specified otherwise.

All safety tables will be presented by centre and overall.

Subjects will be included and counted in summary tables only if they have available data.

For laboratory parameters, vital signs and ECG, baseline will be defined as the last measure prior to fluciclovine (^{18}F) administration including day of administration if available.

6.1 Adverse Events

Adverse events (AE) will be coded using the latest version of the MedDRA dictionary.

A treatment-emergent adverse event (TEAE) is defined as an AE with start date/time on or after the start date/time of ^{18}F -fluciclovine administration, or AEs with worsening intensity on or after the start date/time of ^{18}F -fluciclovine administration, or when the AE has a start time within 1 minute prior to the start time of ^{18}F -fluciclovine administration.

AEs with unknown start date/time will be assumed to be treatment-emergent unless the end date/time is known to be before the ^{18}F -fluciclovine administration.

Summary tables will be produced for all TEAEs occurring up to 42 days after the ^{18}F -fluciclovine administration (i.e. occurring between day 1 and day 43).

An overall summary of TEAEs will be created including:

- number of TEAEs and number of subjects with TEAEs,

- number of TEAEs and number of subjects with TEAEs associated with the injection site,
- number of serious TEAEs and number of subjects with serious TEAEs,
- number of subjects with TEAEs by CTCAE grade (Grade 1 to Grade 5),
- number of subjects with TEAEs by relationship to fluciclovine (definitely, probably, possibly, unrelated)
- number of subjects with TEAEs that are related to or unrelated to fluciclovine, where related TEAEs are those classified as definitely, probably and possibly related

The number and percentage of subjects experiencing TEAEs will be presented by system organ class (SOC) and preferred term (PT). System organ class and preferred term will be presented in decreasing frequency of the total number of subjects with TEAEs. If a subject experienced more than one treatment-emergent adverse event, the subject will be counted once for each system organ class and once for each preferred term.

The number and percentage of subjects experiencing TEAEs will be presented by SOC, PT and CTCAE grade. SOC and PT will be presented in decreasing frequency of the total number of subjects with TEAEs. If a subject experienced more than one TEAE, the subject will be counted once for each SOC and once for each PT at the worst severity.

The number and percentage of subjects experiencing TEAEs will be presented by SOC, PT, relationship to study drug and whether the TEAE is related to the study drug. SOC and PT will be presented in decreasing frequency of the total number of subjects with TEAEs. If a subject experienced more than one TEAE, the subject will be counted once for each SOC and once for each PT at the closest relationship to study drug.

All adverse events will be listed and TEAEs will be identified. AEs occurring up to 42 days after ¹⁸F-fluciclovine administration will be flagged. All SAEs will be listed separately.

6.2 Clinical Laboratory Evaluation

6.2.1 Hematology

Hematology values will be summarised by parameter and visit, and also for change from baseline (last pre-scan value vs first post-scan value).

All haematology values will be listed showing reference ranges (flagging abnormal findings).

6.2.2 Biochemistry

Biochemistry values will be summarised by parameter and visit, and also for change from baseline (last pre-scan value vs first post-scan value).

Additionally, from the serum creatinine levels (mg/dL), creatinine clearance (CrCl) will be derived using the Cockcroft Gault formula (Cockcroft DW, 1976) and the glomerular filtration rate (GFR) will be derived using the modification of diet in renal disease (MDRD) formula (Levey AS, 2006) as follows:

- Cockcroft-Gault formula: $\text{CrCl (mL/min)} = (140 - \text{age}) * (\text{Weight in kg}) * (0.85 \text{ if female}) / (72 * \text{Creatinine})$
- MDRD formula: $\text{GFR (mL/min)} = 175 * \text{Creatinine}^{-1.154} * \text{age}^{-0.203} * 1.212$ (if subject is black) * 0.742 (if female)

CrCl and GFR categories (≤ 30 mL/min, $>30 - \leq 60$, $>60 - \leq 90$, >90 mL/min) will be summarised, and a shift table of baseline status against the status on or after ^{18}F -fluciclovine administration will be presented.

All biochemistry values will be listed showing reference ranges and flagging abnormal findings.

6.2.3 Urinalysis dipstick

All urinalysis results will be listed.

6.3 Vital Signs

Vital sign values will be summarised by parameter and time point, and also for change from baseline.

Details of vital signs data will be listed.

6.4 Electrocardiography

Electrocardiogram (EKG) interpretation is recorded pre-dose/pre-scan and within 7 days of the scan. EKG observed QTc and change from baseline will be summarised by visit. In addition, a summary of the incidence of outliers in absolute QTc intervals (>450 , >480 and >500 msec), and the change from baseline in QTc intervals (>30 and >60 msec both positive and negative changes) will be presented.

The overall interpretation of the EKG (Normal, Abnormal NCS, and Abnormal CS) will also be summarised by visit. All EKG results will be listed, including overall interpretation and change from baseline.

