	
 ○ Whole-body ^{99m}Tc-MDP bone scintigraphy or NaF PET-CT (dependent on standard of care at the institution) and ○ Either CT or MRI of the pelvis (or the abdomen and pelvis). 
 • Being considered for salvage therapy • Any non-surgical local treatment such as previous cryotherapy, external beam radiation, or HiFU must have occurred at least 1 year in the past. • Previous brachytherapy treatment will have occurred at least 2 years in the past • Ability to understand and the willingness to sign a written informed consent 
Exclusion Criteria:
 
 • Ongoing treatment with any systemic therapy intended for the treatment of prostate cancer (e.g., antiandrogen or LHRH agonist or antagonist) • Androgen deprivation therapy (ADT) in the past 3 months • History of bilateral orchidectomy • Inability to tolerate ^{18}F-fluciclovine PET/CT
TEST PRODUCT, DOSE, AND ROUTE OF ADMINISTRATION	
All subjects will receive a single intravenous dose of 10mCi (370MBq) $\pm 20\%$ ^{18}F-fluciclovine immediately prior to PET scan.
 
There will be no repeat dosing

DURATION OF SUBJECT PARTICIPATION AND DURATION OF STUDY	
Patients will be imaged with ^{18}F-fluciclovine PET/CT prior to planned treatment. Follow-up for treatment outcome and results of standard-of-care investigations for up to 6 months after ^{18}F-fluciclovine PET/CT.

CONCOMITANT MEDICATIONS	
Allowed:
 
All treatments except for those specifically prohibited
 
Prohibited:
 
Ongoing treatment with any systemic therapy intended for the treatment of prostate cancer (e.g., antiandrogen or LHRH agonist or antagonist), including bilateral orchidectomy at time of screening or scanning

Efficacy Evaluations	
Primary endpoint	
Change to management plan assessed by comparing Pre-^{18}F-fluciclovine PET/CT management plan with Post-^{18}F-fluciclovine PET/CT management plan.

Secondary endpoint	
1. Per-patient impact (yes/no) of ^{18}F-fluciclovine PET/CT on pre-PET intended versus post-PET actual patient management.

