8.1 Formulation of Test Product

^{18}F -fluciclovine is a radiolabelled synthetic amino acid. The radioactive isotope ^{18}F decays with a half-life of approximately 110 minutes.

Chemical formula

Chemical structure

Chemical name

(anti)-1-amino-3-[¹⁸F]fluorocyclobutane-1-carboxylic acid.

Physiological effects

Biodistribution and radiation dosimetry studies have demonstrated physiological uptake of ¹⁸F-fluciclovine to be highest in the liver and pancreas, with rapid biological clearance. (9) There is low albeit prolonged uptake in skeletal muscle and bone marrow, with clearance dominated by the tracer half-life. (9)

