10.3 Visit 2 – ¹⁸F-fluciclovine PET-CT

Prior to the dose of ¹⁸F-fluciclovine and the PET/CT scan, the following assessments will be performed:

1. Review and update the Subject's medical history to check for new health-related events and changes to concomitant medications since the Screening visit.
2. Ensure treatment plan has been documented prior to ¹⁸F-fluciclovine PET/CT;
3. Obtain vital signs.
4. Obtain blood sample for:)
 - o Hematology)
 - Biochemistry) Unless obtained at screening
5. 12-lead EKG)
6. Obtain a urine sample and perform dipstick analysis.)
 - o If the results are abnormal these are to be recorded and the Subject is to proceed to having the fluciclovine PET/CT

Dosing and PET/CT Procedure: A venous cannula will be inserted and the Subject will receive one dose of ¹⁸F-fluciclovine. Subjects will be imaged starting 4 minutes after injection from proximal-thigh to skull base. The duration of the scan is approximately 25 minutes on the PET/CT scanner.

Following the scan, Subjects will be encouraged to drink water to encourage hydration and frequent voiding to reduce radiation dose from ¹⁸F-fluciclovine excretion. The following assessments will be performed

1. Obtain blood sample for:)
 - a. Hematology)
 - b. Biochemistry) Unless to be obtained in the next 7 days
2. 12-lead EKG)
3. Obtain vital signs immediately post scan and at 60 (± 5) minutes, and 120 (±5) minutes post-injection.
4. Assess the Subject for adverse events at 30 minutes, 60 minutes, and 120 minutes post-injection.

10.4 Visit 3 - Telephone Consultation at 24 - 72 (+/- 4) hours after dosing

An adverse event evaluation will be performed at **24 - 72 hours** (± 4 hours) after ¹⁸F-fluciclovine administration via telephone consultation.

10.5 Documentation of Management plan revision post ¹⁸F-fluciclovine PET/CT Scan (2-22 days following the scan)

The treating physician will complete the Management Plan Questionnaire to document changes to the Pre-Scan Management Plan. A copy of the Questionnaire must be maintained in the Subject's medical record.

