3.3 Visit Structure

The visit structure and scheduled assessments are detailed in Appendix 1: Schedule of Events of the protocol.

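### SAP 6.4 summarises post-dose QTc by visit although the EKG may be taken on the scan day or up to 7 days later, so a transient acute effect could be attenuated in the table

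*SAP*

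**What the plan says.** Protocol 5.3 names change from baseline in QTc as a safety evaluation. Exposure is one injection; the synopsis states "There will be no repeat dosing".

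- **Timing of the post-dose EKG.** Protocol 10.3 lists post-scan blood samples and a 12-lead EKG with the proviso "Unless to be obtained in the next 7 days". Appendix 1, footnote 3, is explicit that this covers the EKG: "Post-dose blood tests and EKG may be performed at the Imaging Center or within 7 days of the scan at another laboratory/site". The footnote is attached to the column for assessments immediately after the scan. No other post-dose EKG is scheduled.
- **Visits used in the analysis.** SAP 3.3 defers to the same schedule: "The visit structure and scheduled assessments are detailed in Appendix 1: Schedule of Events of the protocol".
- **QTc analysis.** SAP 6.4 repeats the window (the EKG "interpretation is recorded pre-dose/pre-scan and within 7 days of the scan") and then says "EKG observed QTc and change from baseline will be summarised by visit". It adds one set of outlier counts: absolute QTc above 450, 480 and 500 msec, and changes of more than 30 and 60 msec in either direction.
- **Laboratory analysis.** SAP 6.2 compares "last pre-scan value vs first post-scan value", whatever the day of the post-scan sample.
- **Vital signs.** SAP 6.3 summarises these by time point, matching the fixed times in Protocol 10.3.

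Neither document splits the QTc summaries by time since injection, restricts them to same-day EKGs, or plans a sensitivity analysis by timing.

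**The concern.** The post-dose EKG is there to show whether QTc changes after the injection. An EKG recorded shortly after the scan and one recorded several days later answer different questions, yet the plan gives them the same label and pools them.

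If a QTc effect were acute and short-lived, late EKGs would show little of it. A mean change near zero, or few outliers, could then mean either that there is no effect or that many EKGs were recorded too late to show one. The planned table could not separate the two explanations, because it does not report how many EKGs fall on each side. For a transient effect the error runs towards reassurance, which is the less safe direction for a safety table.

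**Working it through.** The documents state no expected QTc effect, standard deviation, power or sample size for this evaluation, so there is no figure of the plan's own to reproduce. The check is a simple mixture calculation.

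**Inputs**

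- From the documents: a single dose; a post-dose EKG on the scan day or up to 7 days later; QTc summarised by visit with no split by time.
- Assumed, because the documents do not give them: f, the share of post-dose EKGs recorded after the scan day; d, the acute mean QTc effect, set at 10 msec; the SD of QTc change, set at 15 or 20 msec; normally distributed changes; and an effect that is zero by the time of the later EKGs.

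**Formulas**

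- Pooled mean change = (1 − f) × d.
- Pooled rate of increases above 30 msec = (1 − f) × P(change > 30 | mean d) + f × P(change > 30 | mean 0).

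**Rates at the two extremes**

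- SD 15: with the effect, 1 − Φ((30 − 10)/15) = 9.1%; without it, 1 − Φ(30/15) = 2.3%.
- SD 20: with the effect, 1 − Φ((30 − 10)/20) = 15.9%; without it, 1 − Φ(30/20) = 6.7%.

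**Results with d = 10 msec**

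| f | Pooled mean change (msec) | Increases > 30 msec, SD 15 | Increases > 30 msec, SD 20 |
|---|---|---|---|
| 0% | 10.0 | 9.1% | 15.9% |
| 25% | 7.5 | 7.4% | 13.6% |
| 50% | 5.0 | 5.7% | 11.3% |
| 75% | 2.5 | 4.0% | 9.0% |
| 90% | 1.0 | 3.0% | 7.6% |

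The excess over the no-effect rate shrinks by the same factor as the mean. At SD 15 and f = 50% the excess is 5.70 − 2.28 = 3.42 points, half of the same-day excess of 9.12 − 2.28 = 6.84 points.

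The factor (1 − f) does not depend on d or the SD, but the msec and percentage figures do. At f = 0 nothing is lost.

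**What the half-life adds.** Protocol 8.1 says the isotope "decays with a half-life of approximately 110 minutes". Seven days is 7 × 24 × 60 = 10,080 minutes, and 10,080/110 is about 92 half-lives. This measures remaining radioactivity only, and the calculation above does not use it.

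**The case against.** **Pooling is partly inferred.** The table shells are a separate document and might split by timing. However, the SAP text specifies no split, and the schedule it adopts has one post-dose EKG entry. An analyst following the SAP as written would pool.

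**There are other safeguards.** SAP 6 presents safety tables by centre, which would partly expose late recording if it follows site practice. All EKG results are listed. Vital signs and adverse events are checked at fixed times on the scan day. These help a careful reader, but none of them corrects the QTc mean or the outlier counts.

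**EKG safety is descriptive.** There is no hypothesis, and neither document contains a planned conclusion on QTc. The 7-day window is also stated openly in SAP 6.4. This stands, and it keeps the point minor.

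**A reader might infer that laboratory effects are diluted too.** The documents do not support that. A delayed change may show better in a later sample, and Protocol 8.1 mentions prolonged low uptake in bone marrow as well as rapid clearance. Pooling mixes times for laboratory values, but the direction of any distortion is unknown.

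**A reader might infer from the 110 minutes that a day-7 EKG carries no information on an acute effect.** That is plausible but not documented. The figure is the isotope's physical half-life. It is neither the elimination half-life of the compound nor the duration of any QTc effect.

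**Conclusion.** The point holds for QTc as a minor gap in the safety analysis. As written, the plan can combine EKGs recorded minutes and days after one injection. A transient acute effect, or its excess outlier rate, would then appear at about (1 − f) of its same-day size.

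This rests on two assumptions: that some EKGs are recorded after the scan day, and that the effect has gone by then. Because f is not in the documents, attenuation is possible but not shown. The 10 msec effect and the SDs are illustrations, not expected values. It would go too far to say that the plan does dilute QTc findings, or that it dilutes laboratory findings. The primary endpoint is not affected.

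**What to change.** In SAP 6.4, present observed QTc, change from baseline and the outlier counts separately for EKGs recorded on the day of injection and for those recorded later, up to 7 days. Give the number of subjects in each group, and base any statement on acute QTc effect on the same-day group.

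For hematology and biochemistry (SAP 6.2) the same split is optional and purely descriptive.

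The cost is an extra column or two per table, with no new procedure or visit. Protocol 8.5 puts the date and start/stop times of the injection on the eCRF, so a split by day needs only the date of each EKG. Neither document says that EKG clock times are captured. A split by date would still mix minutes with hours, so times should be used if they exist. Each group will be smaller than the whole, and the groups may differ by site; they should therefore be described side by side and not compared.
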